#### 7.6.1.6.2 Analysis of Menopause-Specific Quality of Life

The observed value and change from baseline to week 12 and week 52 for MENQOL total score and scores for each domain (vasomotor, psychosocial, physical, and sexual functioning) will be summarized by using descriptive statistics including number of subjects (n), mean, SD, median, min, and max and 95% CIs for the Safety Analysis Set and PP Analysis Set. Visits

---

will be clustered as specified in [Table 5](#) of Appendix 1.

A listing will be provided for MENQOL questionnaire data for the Included Set.

#### **7.6.1.7 Clinical Global Impression Questionnaire**

Subjects will answer the question 'Rate total improvement whether or not, in your judgement, it is due entirely to drug treatment. Compared to your condition at administration to the study, how much has it changed' using the following categorical scale:

- Very much improved
- Much improved
- Minimally improved
- No change
- Minimally worse
- Much worse
- Very much worse

Total score improvement after 4, 12 and 52 weeks of treatment using the CGI questionnaire will be summarized using number (n), percentage and percentage 95% CIs in each category for the Safety Analysis Set and PP Set.

A listing will be provided for CGI questionnaire data for the Included Set.

#### **7.6.1.8 Analysis of Exploratory Endpoint**

Not applicable

### **7.7 Safety Analyses**

The safety evaluations will include analyses of TEAEs, physical and gynecological examination, breast examination, vital signs, ECG, routine clinical laboratory tests and mammography. For all safety endpoints, visits will be clustered as specified in [Table 6](#) and [Table 7](#) of Appendix 1.

The safety analyses involving changes from baseline to a specific time point for safety variables (e.g., laboratory parameters, vital signs, and ECG) will only include subjects from the Safety Analysis Set who have data available for both the baseline and the time point under consideration unless otherwise specified.

All safety evaluations will be summarized using data from the Safety Analysis Set if not indicated otherwise. No formal statistical test will be performed. Continuous variables will be summarized using descriptive statistics (n, mean, SD, median, min, max), categorical variables will be presented in frequency tables using counts and percentages.

#### **7.7.1.1 Adverse Events**

All AE verbatim descriptions will be coded using the MedDRA, version 24.1 or the most updated version.

---

All AEs will be listed, TEAEs will be summarized as definition of TEAE are described in [Section 6.1](#). Details for imputing missing or partial start dates of AEs are described in Section 6.2.2.

In summaries by SOC and PT, TEAEs will be sorted by decreasing frequency within each SOC and PT. In summaries by PT, TEAEs will be sorted by decreasing frequency.

If a subject experiences the same TEAE more than once with different intensities, then the event with the highest intensity will be tabulated in 'by intensity' tables. TEAEs with a missing intensity will be presented in the summary table as an intensity category of 'Missing'.

If a subject experiences multiple TEAEs within the same PT (SOC), then the subject will be counted only once for that PT (SOC).

Relationship to study drug, as indicated by the Investigator, is classified as 'Highly probable', 'Probable', 'Possible', 'Unlikely' and 'Not Related'. If a subject experiences multiple TEAE within the same PT(SOC), the TEAE with the strongest relationship to study drug will be counted for that PT(SOC). Relationship will be summarized as 'Related' and 'Not Related'. Adverse Events with investigator indicated drug-event relationship of 'Unlikely' and 'Not Related' will be classified as 'Not Related' to study drug, while Adverse Events with drug-event relationship documented as 'Highly probable', 'Probable', 'Possible' will be considered as 'Related' to study drug. Where TEAEs have a missing relationship to study drug will also be considered as 'Related' to study drug.

Adverse Events of Special Interest (AESI) are a subset of TEAEs that include the events listed below:

- Vaginal bleeding events grade 2 as assessed using the vaginal bleeding events scale
  - Events resulting from endometrial biopsy reading limited to:
    - Disordered proliferative endometrium;
    - Simple hyperplasia without atypia;
    - Complex hyperplasia without atypia;
    - Simple hyperplasia with atypia;
    - Complex hyperplasia with atypia;
    - Carcinoma

Collecting and recording AESIs will begin on Treatment Start Date and will end at the follow-up visit. AESI collection will start at each site from the date of the Ministry of Health and/or Institutional Review Board (IRB)/Ethics Committee (EC) approval date of Protocol Version 6.0 (Amendment 5). There will not be any retrospective reporting.

An overview of TEAEs will be presented for the Safety Analysis Set with the frequency counts and percentages of subjects with at least one:

- TEAE;
- Severe TEAEs;
- Drug related TEAEs;

- Serious TEAE;
- Drug related serious TEAEs;
- TEAEs leading to dose interruption;
- TEAEs leading to study drug discontinuation;
- TEAEs leading to death;
- Drug related TEAEs leading to death;
- AESI

The overview table will also be presented by hysterectomy status (hysterectomized and non-hysterectomized).

All TEAEs (including AESI and SAE), SAE (including serious AESI) and AESI (including both serious and non-serious AESI) will also be summarized for the Safety Analysis Set as below:

- TEAEs by SOC, PT;
- TEAEs of reproductive system and abdominal pain by SOC, PT by hysterectomy status (hysterectomized and non- hysterectomized), as defined in [Table 4](#);
- TEAEs by SOC, PT and maximum intensity;
- TEAEs of reproductive system and abdominal pain by SOC, PT and maximum intensity by hysterectomy status (hysterectomized and non- hysterectomized), as defined in [Table 4](#);
- Drug related TEAEs by SOC, PT and maximum intensity;
- Drug related TEAEs of reproductive system and abdominal pain by SOC, PT and maximum intensity by hysterectomy status (hysterectomized and non- hysterectomized), as defined in [Table 4](#);
- TEAEs leading to study drug interruption by SOC, PT, and maximum intensity;
- TEAEs of reproductive system and abdominal pain that leading to study drug interruption by SOC, PT and maximum intensity by hysterectomy status (hysterectomized and non-hysterectomized), as defined in [Table 4](#);
- TEAEs leading to study drug discontinuation by SOC, PT, and maximum intensity;
- TEAEs of reproductive system and abdominal pain that leading to study drug discontinuation by SOC, PT and maximum intensity by hysterectomy status (hysterectomized and non- hysterectomized) ), as defined in [Table 4](#);
- Serious TEAEs by SOC, PT;
- Serious TEAEs of reproductive system and abdominal pain by SOC, PT by hysterectomy status (hysterectomized and non- hysterectomized), as defined in [Table 4](#);
- Serious TEAEs by SOC, PT and maximum intensity;
- Serious TEAEs of reproductive system and abdominal pain by SOC, PT and maximum intensity by hysterectomy status (hysterectomized and non- hysterectomized), as defined in [Table 4](#);
- Drug related serious TEAEs by SOC, PT and maximum intensity;
- Drug related serious TEAEs of reproductive system and abdominal pain by SOC, PT and maximum intensity by hysterectomy status (hysterectomized and non- hysterectomized), as defined in [Table 4](#);

- TEAEs leading to deaths, by SOC, PT and maximum intensity;
- TEAEs of reproductive system and abdominal pain that leading to deaths, by SOC, PT and maximum intensity by hysterectomy status (hysterectomized and non- hysterectomized), as defined in [Table 4](#);
- Drug related TEAEs leading to deaths, by SOC, PT and maximum intensity;
- Drug related TEAEs of reproductive system and abdominal pain that leading to deaths, by SOC, PT and maximum intensity by hysterectomy status (hysterectomized and non-hysterectomized), as defined in [Table 4](#);
- AESI by SOC, PT and hysterectomy status (hysterectomized and non- hysterectomized);
- AESI by SOC, PT and maximum intensity and hysterectomy status (hysterectomized and non-hysterectomized);
- Venous thromboembolism events (VTE) incidence and cardiovascular events incidence, with additional information as defined below:

Number of Subjects with at least one event in each of the following categories:

- VTE including:
  - Pulmonary embolism and Pulmonary embolus.
  - Deep venous thrombosis.
- Cardiovascular events including:
  - Myocardial infarction, Acute myocardial infarction and Myocardial ischaemia.
  - Cerebrovascular accident, Transient ischaemic attack, Ischaemic stroke and Subarachnoid haemorrhage.
  - Peripheral occlusive disease.
  - Angina unstable and Angina pectoris terms
- Other thrombotic events

Number of VTE and CV events, n per 1000 patient-years (n/1000 PY) of exposure will be presented, which is defined as the summation of number of years for all the subjects at risk, calculated as:

$$\text{Events per 1000 Patient-Years} = n / PY * 1000$$

where,

n = number of events in each group.

PY = (End of Treatment Date – First treatment date + 1)/365.25 or

(cut-off date – First treatment date + 1)/365.25 for ongoing subjects.

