10.6. Adverse Events of Special Interest

AESIs are a subset of AEs that include the events listed below:

- Vaginal bleeding events grade 2 as assessed using the vaginal bleeding events scale (see section 10.4.9);
- Events resulting from endometrial biopsy reading limited to:

- Disordered proliferative endometrium;
- Simple hyperplasia without atypia;
- Complex hyperplasia without atypia;
- Simple hyperplasia with atypia;
- Complex hyperplasia with atypia;
- Carcinoma.

In order to facilitate the documentation of AESIs in the eCRF, the event term on the report should be listed as above. In addition, a standard questionnaire will be available to investigators in the eCRF in the SAE screen as guidance on the information to be reported.

The standard time period for collecting and recording of AESIs will begin at the first intake of study drug/placebo and will end at EoT visit. AESIs will be reported to the Sponsor within the same timeframes described for SAEs. AESI collection should start as of the Ministry of Health and/or IRB/EC approval date of Protocol Version 6.0 (Amendment 5). There is no need for retrospective reporting.

Once an onset of a new AESI or exacerbation of a pre-existing AESI is identified (serious or non-serious) in a study subject, the investigator (or designee) must complete the information in the SAE screens of the eCRF **WITHIN 24 HOURS** after he/she becomes aware of the diagnosis. A field on the SAE screen allows to specify that the event is an AESI and whether it is serious or non-serious. These screens will always be completed as thoroughly as possible with all available details of the event, in accordance with the AESI standard questionnaire provided in the eCRF. Even if the investigator does not have all information regarding an AESI, the screens should still be completed within 24 hours. Once additional relevant information is received regarding the AESI, the eCRF should be updated **WITHIN 24 HOURS**. The investigator will always provide an assessment of causality at the time of the initial report.

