### 5.3 Safety Analysis Set

The Safety Analysis Set will include all subjects who receive at least one dose of study drug. The Safety Analysis Set will be used for all analyses of efficacy, safety, tolerability, and background characteristics.

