#### **7.7.1.13 Vaginal Bleeding and/or Spotting**

Absence or occurrence of vaginal bleeding and/or spotting on a daily basis will be assessed using the scale below:

- 0 = Absence of vaginal bleeding or spotting;
- 1 = Spotting: evidence of minimal blood loss requiring none or at most one pad, tampon or panty liner per day;
- 2 = Bleeding: evidence of blood loss requiring more than one pad, tampon or panty liner per day.

Frequency counts (n) and percentage of subjects with absence of any bleeding and/or spotting during the cycle, with vaginal bleeding and/or spotting during the cycle, with bleeding only during the cycle, with spotting only during the cycle will be provided for each 28- day cycle of treatment based on data in the subject diary (in non-hysterectomized subjects) for the Safety Analysis Set.

The number of days with bleeding or spotting, as reported on subject diaries, will be summarized by 28-day cycle of treatment.

A listing will be provided for vaginal bleeding and/or spotting and/or amenorrhea for the Included Set.

The following data will be excluded from analysis of endpoints for bleeding (to be analysed separately)

- bleeding for the day on which an endometrial biopsy was performed and 6 days after biopsy and
- bleeding reported after discontinuation of study drug (for example withdrawal bleeding, on P4 treatment)

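### AESI collection ends at different visits in protocol and SAP, and the AESI percentage counts women treated before AESI recording began

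*SAP*

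**What the plan says.** **End of collection.** Protocol 10.6 states that AESI collection "will begin at the first intake of study drug/placebo and will end at EoT visit". SAP 7.7.1.1 states: "Collecting and recording AESIs will begin on Treatment Start Date and will end at the follow-up visit".

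**Start of collection.** Protocol 10.6 adds a calendar condition: "AESI collection should start as of the Ministry of Health and/or IRB/EC approval date of Protocol Version 6.0 (Amendment 5". The SAP applies the same condition site by site and adds: "There will not be any retrospective reporting".

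**Statistic and denominator.** SAP 7.7.1.1 describes the overview table, which has an AESI row, as follows: "An overview of TEAEs will be presented for the Safety Analysis Set with the frequency counts and percentages of subjects with at least one". SAP 5.3 defines that set: "The Safety Analysis Set will include all subjects who receive at least one dose of study drug". A further table is "AESI by SOC, PT and hysterectomy status (hysterectomized and non- hysterectomized". None of these carries a restriction, flag or footnote for treatment given before AESI recording began.

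**Related bleeding rule.** SAP 7.7.1.13 takes out of the bleeding endpoints, for separate analysis, "bleeding reported after discontinuation of study drug (for example withdrawal bleeding, on P4 treatment". No corresponding rule is given for grade 2 bleeding reported as an AESI.

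**The concern.** A proportion of subjects with at least one event can be read only if numerator and denominator refer to the same observation period. Here the numerator has two possible closing dates and a late calendar start, while the denominator is every woman who took a dose.

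The closing date matters because non-hysterectomized women take P4 for 14 days after EoT and go on recording bleeding. Grade 2 bleeding in that time is an AESI under the SAP window and not under the protocol window.

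The start matters because non-hysterectomized women could enter the Safety Study part from Protocol 5.0, before AESIs were defined in Protocol 6.0. A woman treated in between stays in the denominator for her whole treatment but has AESI reports for only part of it, or for none.

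At stake is a descriptive safety figure that will be quoted in its own right for an unopposed estrogen in women with a uterus.

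**Working it through.** The plan states no AESI rate, expected count or precision, so there is no figure to reproduce.

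**1. Is the difference in closing date real?** Protocol 10.6 is current text. The summary of changes for Amendment 6.1 shows the same end in Protocol 7.1, the version on which the SAP says it is based. SAP section 8 lists three departures from the protocol, all about analysis sets. The later end does agree with the SAP's own TEAE definition (Table 1), which runs to the follow-up visit for non-hysterectomized women.

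**2. Length of the gap.** Inputs (Protocol Table 4): EoT Day 365–371, follow-up Day 379–392.
- Shortest: 379 − 371 = 8 days. Longest: 392 − 365 = 27 days.
- Nominal: 14 days of P4 plus about 10 days = about 24 days, inside that range.

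**3. What the gap could do.** Assume a 20% AESI risk up to EoT and an independent risk w of grade 2 bleeding after EoT. The risk to follow-up is 1 − (1 − 0.20)(1 − w):

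| w (assumed) | Risk to follow-up |
|---|---|
| 5% | 24% |
| 10% | 28% |
| 20% | 36% |

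**4. How much treatment could precede AESI recording.** Inputs (Protocol 1.6): version 5.0 dated 3 February 2020, version 6.0 dated 23 September 2020.
- Interval: 233 days, or 233 − 28 = 205 after a four-week screening period.
- Share of a 371-day treatment: 205/371 = 55% to 233/371 = 63%.

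These are version dates. Approval lags at the sites are not given.

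**5. Effect on the percentage.** Let p be the true risk over treatment in non-hysterectomized women, s the share of them first dosed before local approval, and u the share of those women's treatment that precedes it. With a constant hazard, the reported risk is (1 − s)p + s[1 − (1 − p)^(1 − u)]. All three inputs are assumptions. For p = 20%:

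| s | u | Reported |
|---|---|---|
| 0 | any | 20.0% |
| 10% | 0.55 | 19.0% |
| 25% | 0.55 | 17.4% |
| 50% | 0.55 | 14.8% |
| 50% | 1.00 | 10.0% |

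Worked row: 0.80^0.45 = 0.9045, so a partly captured woman has risk 9.55%, and 0.5 × 20% + 0.5 × 9.55% = 14.8%. Over p = 5–30%, s = 0–50% and u = 0.25–1, the relative understatement runs from 0% to 50%.

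**6. Direction.** Step 5 lowers the percentage. Step 3 raises the SAP-window figure relative to the protocol-window figure. The net effect cannot be signed.

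**The case against.** **The percentage has not been shown to be wrong.** A reader might infer that it is. The documents do not support that, because they give no first-dose dates, approval dates or AESI rate. If every non-hysterectomized woman in this part was first dosed after local approval, the late start costs nothing. This stands.

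**Lost time is not lost subjects.** A reader might scale the percentage down by the share of exposure before approval. That does not fit an at-least-one-event count, since a woman with a later or recurrent event still counts. A woman dosed on 3 February 2020 itself would reach Day 365 after 364 days, which is 364 − 233 = 131 days after the date of version 6.0. Her EoT biopsy would fall before AESI recording only with a longer approval lag. Complete non-capture is therefore mainly a matter of early discontinuers. This stands too.

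**EoT biopsy findings are not lost.** A reader might infer that closing collection at EoT drops the biopsy taken that day. Protocol 10.4.8 and 10.4.10 require disordered proliferative endometrium or worse to be reported as an AESI without a time limit, and Protocol 10.6 counts its 24 hours from awareness of the diagnosis. Loss is not established. What remains is that neither document says whether biopsy date or reading date governs.

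**Sites follow the protocol, not the SAP.** True, and AEs are recorded at the follow-up visit anyway. But then a table described as running to follow-up may be filled from AESI reports that stopped at EoT, and a low count after EoT could be misread.

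**The bleeding exclusion has another purpose.** A diary endpoint limited to time on treatment and an AE table that includes follow-up can coexist, and the SAP does say the excluded bleeding is analysed separately. The contrast is a reason to split the AESI table at EoT. It is not a contradiction in itself.

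**Other outputs hold the information.** All AEs from consent are recorded, and AESIs are defined as a subset of TEAEs, so earlier events may be recoverable by term. The SAP does not say that this will be done, and AESI status is entered in a dedicated eCRF field. The remedy is therefore cheap, but it is not yet in the plan.

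**Conclusion.** The concern holds in a limited form. The two documents close AESI collection at different visits, 8 to 27 days apart on the scheduled windows, and SAP section 8 does not record this. Both start collection at approval of Protocol 6.0 without back-filling, while the percentage uses all treated subjects.

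Two things follow. The AESI percentage may be understated for non-hysterectomized women treated wholly or partly before local approval, by an amount that the documents do not allow anyone to calculate and that is zero if there were no such women. And it is not comparable between the two windows. The percentages shown above rest on assumed risks and shares and a constant hazard; they illustrate scale only.

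The endometrial endpoint uses consensus pathology and the bleeding endpoints use the diary, so neither is affected. Only the SAP for the Safety Study part was available, so nothing is concluded about AESI tables for the Efficacy Study part.

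**What to change.** 1. Reconcile Protocol 10.6 with SAP 7.7.1.1 on the end of AESI collection, and record any remaining difference in SAP section 8.
2. State that an endometrial AESI is assigned by the date of the biopsy, whenever it is read.
3. Tabulate AESIs up to EoT and after EoT separately.
4. Deal with the late start in one of two ways:
   - give the AESI percentage, as the main display or as a sensitivity table, for non-hysterectomized women first dosed on or after local approval of Protocol 6.0. The criterion must be first dose: requiring only some exposure after approval would keep partly captured women in; or
   - classify the listed AESI terms from all recorded TEAEs for every non-hysterectomized woman. This keeps the full denominator but recovers only events that sites entered as AEs before version 6.0.

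The cost is SAP wording plus one extra table or derivation from existing data. The restricted display has a smaller denominator and so a less precise percentage. Rewording the protocol cannot change collection already completed, so items 3 and 4 carry most of the benefit.

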8. SUBJECT SELECTION AND DISCONTINUATION/WITHDRAWAL OF SUBJECTS

8.1. Source and Number

This will be a multicenter trial performed in multiple study sites in the United States of America and Canada. Subjects will be recruited by the investigator from his/her patients or will be recruited by recruitment campaigns. Subjects must seek treatment for the relief of menopausal symptoms, or subject may already be treated for menopausal symptoms and willing to discontinue their current treatment.

All investigators must keep a record of subjects who were considered for enrollment and were consented, but were never enrolled e.g., subject screening log to address concerns over selection bias.

This trial will enroll a total of approximately 1,000 subjects; ~600 subjects ~200 per treatment arm) in the Efficacy Study part and ~400 subjects in the Safety Study part of the trial. Enrollment will stop when the minimum required number of subjects in each study group and study part is enrolled.

The number of completers after three months of treatment in the Efficacy Study part is anticipated to be around 435, anticipating a drop-out rate of 35% and 20% for non-hysterectomized and hysterectomized women, respectively. The number of completers after 12 months of treatment is anticipated to be ~300, anticipating a drop-out rate of 50% after one year of treatment.

The number of completers in Safety Study part after 12 months of treatment is expected to be ~200, anticipating a drop-out rate of 50%.

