8.1.1. Justification of Sample Size

Efficacy Study part: based on results observed for the E4 15 mg dose in the Phase 2 study, a sample size of ~200 subjects per arm provides a power of at least 80% to simultaneously achieve a superiority (upper bound of a 95% 2-sided confidence interval [CI] lower than zero) over placebo for the four co-primary endpoints together. This sample size accounts for a dropout rate during the first 12 weeks of the study of 35% and 20% for non-hysterectomized and hysterectomized women, respectively.

It is planned to enroll approximately 100 hysterectomized and 100 non-hysterectomized subjects per treatment arm.

Safety Study part: the target number of ~400 subjects has been selected to fulfill the requirement stated in International council for harmonization of technical requirements for pharmaceuticals for human use (ICH) E1 guideline (CPMP/ICH/375/95) regarding number of subjects exposed to the drug for safety assessments.

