## **3 STUDY DESIGN**

### **3.1 General Study Design**

This study is a Phase III study, with multiple centers in the USA and Canada. Eligible subjects will be post-menopausal women,  $\geq 40$  up to  $\leq 65$  years of age, seeking treatment for relief of moderate to severe vasomotor symptoms (VMS) associated with menopause.

The Safety Study part will be conducted in approximately 200 hysterectomized and approximately 200 non-hysterectomized postmenopausal women, who are seeking treatment for the relief of VMS (condition clinically indicated by the investigator) associated with menopause and have at least 1 moderate to severe VMS symptom per week.

The Safety Study part is an open label study, to evaluate the effect of E4 20 mg (Arm 4) on the primary safety and secondary efficacy endpoints (lipid and glucose metabolism, HRQoL and TS) over a 52 week treatment period. For endometrial protection, all non-hysterectomized subjects will receive treatment with 200 mg progesterone (P4) once daily for 14 consecutive days, after completion of the E4 treatment. The target number of subjects to be included in the Safety Study part is approximately 400. Enrollment in the Safety Study part will stop as soon as the minimum required number of subjects in each study group and study part is enrolled.

[figure not shown]
At least 8 visits (up to 15 months) are planned in the Safety Study part, this includes:

- Washout visit (occurring generally up to 8 weeks prior to Screening visit),
- Screening visit (occurring 4 weeks prior to Baseline [Visit 1]),
- Treatment visits (occurring within 53 weeks; Visit 1 to Visit 6), include:
  - Baseline (Visit 1),
  - Five On-treatment visits (Visits 2, 3, 4, 5 and 6), the last treatment visit (Visit 6) is also the end of treatment (EoT) visit, which will also occur in case of early discontinuation.

For non-hysterectomized women an additional endometrial safety follow-up visit (visit 7) is planned approximately 10 days after completion of the 14 days of P4 treatment, which will also occur in case of early discontinuation

The trial schedule for Safety Study part is summarized in [Figure 1](#).

Figure 1: Trial Schedule

EoT = End of Treatment; NH = Non-hysterectomized; H = Hysterectomized; E4 = estetrol; P4 = progesterone

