**4 SAMPLE SIZE AND POWER**

The target number of subjects to be included in the Safety Study part is approximately 400.

Enrollment will stop when the minimum required number of subjects in each study group and study part have been enrolled. The number of subjects has been selected to fulfill the requirement stated in ICH E1 guideline (CPMP/ICH/375/95) regarding number of subjects exposed to the drug for safety assessments.

---

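### Apart from VTE and cardiovascular events, the Safety part reports TEAEs, serious TEAEs and AESIs only as crude percentages although 50% dropout is expected; exposure-adjusted rates would be a cheap addition.

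*SAP*

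**What the plan says.** The first of three endpoints under the Safety part's primary objective is the frequency of TEAEs, including serious ones (SAP 2.1). The other two cover changes in examinations and in laboratory tests, and these are handled mainly by shift tables and change from baseline.

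For TEAEs, SAP 7.7.1.1 says: "An overview of TEAEs will be presented for the Safety Analysis Set with the frequency counts and percentages of subjects with at least one" of each event type listed, AESIs included. Under SAP 5.3 the Safety Analysis Set is everyone with at least one dose. The SAP adds that "The overview table will also be presented by hysterectomy status". The AESI tables and the reproductive-system and abdominal-pain tables are also split by status; the general SOC/PT tables are not. Person-time appears once in the adverse-event section: "Number of VTE and CV events, n per 1000 patient-years (n/1000 PY) of exposure will be presented".

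On size and retention, "The target number of subjects to be included in the Safety Study part is approximately 400" (SAP 4), split about 200 and 200 by hysterectomy status (SAP 3.1). Protocol 8.1 says "The number of completers in Safety Study part after 12 months of treatment is expected to be ~200, anticipating a drop-out rate of 50" per cent. It gives no split of that figure by status. The only split, "35% and 20% for non-hysterectomized and hysterectomized women, respectively", is for the first 12 weeks of the Efficacy part.

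SAP Table 1 closes the TEAE window at the end-of-treatment or early-discontinuation visit, but at the follow-up visit for non-hysterectomized women.

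**The concern.** When half the women are expected to leave during a 52-week treatment period, the percentage with at least one event mixes two things: how often events occur and how long women were watched. The Safety part is there to describe up to a year of E4 20 mg, so a reader will tend to take the percentage as a 12-month risk. No formal test is planned, so the descriptive estimate is the whole result.

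The display by hysterectomy status adds a second difficulty. The two columns cover different observation windows and may cover different treatment durations, with no adjustment for either.

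**Working it through.** **1. The plan's own figure.** Completers = 400 × (1 − 0.50) = 200, as Protocol 8.1 states. The Efficacy-part figures also reproduce: 300 × 0.65 + 300 × 0.80 = 435 at three months, and 600 × 0.50 = 300 at 12 months.

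**2. Mean exposure.** Assume a constant dropout rate reaching d = 50% at one year. Then h = −ln(1 − 0.5) = 0.693 per year and mean exposure is d/h = 0.5/0.693 = 0.72 year. For 400 women that is about 289 patient-years rather than 400.

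**3. Crude percentage against true 12-month risk R.** Assume a constant event rate λ = −ln(1 − R), unrelated to dropout. Then crude = λ/(λ + h) × [1 − exp(−(λ + h))]. For R = 10%, λ = 0.105 and λ + h = 0.799, so crude = 0.105/0.799 × (1 − 0.45) = 7.3%.

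| True 12-month risk | Crude percentage | Ratio |
|---|---|---|
| 2% | 1.4% | 0.72 |
| 10% | 7.3% | 0.73 |
| 20% | 14.6% | 0.73 |
| 30% | 22.1% | 0.74 |
| 50% | 37.5% | 0.75 |

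**4. Sensitivity to when women leave.** If all leavers go at time t, crude = 0.5 × [1 − exp(−λt)] + 0.5 × R. For R = 10%:
- Week 12: 0.012 + 0.05 = 6.2%
- Week 26: 0.026 + 0.05 = 7.6%
- Week 40: 0.039 + 0.05 = 8.9%

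**5. What a rate would recover.** In step 3, 400 women give about 29.0 first events over 275.5 at-risk patient-years, or 10.5 per 100 patient-years. Converting back, 1 − exp(−0.105) = 10%.

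**6. By hysterectomy status.** No Safety-part split exists, so every scenario here is an assumption. Each takes an identical true risk of 10% in both groups.

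- *Efficacy-part split borrowed.* Retention at Week 12 is 0.80 and 0.65 (mean 0.725). A common later rate then brings overall retention to 0.50, a factor of 0.50/0.725 = 0.690. One-year retention is 55% (hysterectomized) and 45% (non-hysterectomized), and mean exposure is 0.72 and 0.61 year. Crude figures are 7.2% and 6.1%.
- *Same, with the longer window.* Add about 24 days (14 days of P4 plus about 10) for non-hysterectomized women, assuming all attend follow-up. Their figure becomes 0.061 + (1 − 0.061) × [1 − exp(−0.105 × 24/365.25)] = 6.7%, against 7.2%.
- *Equal 50% dropout in both groups, with the longer window.* Hysterectomized women show 7.3%. Non-hysterectomized women show 0.073 + (1 − 0.073) × 0.0069 = 7.9%.

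The ordering reverses between the second and third scenarios. The documents do not say which is closer to the Safety part.

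**The case against.** The endpoint is worded as a frequency, and Protocol 12.8 prescribes counts and percentages for categorical safety data. The SAP therefore does what the protocol asks. That stands: this is an improvement, not a departure from the protocol.

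A reader might infer that the whole primary objective rests on crude percentages. It does not. Two of its three endpoints are summarised in other ways, and VTE and cardiovascular events have patient-year rates.

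A reader might also infer that the percentages understate risk outright. The documents do not support that without conditions. It holds when the percentage is read as a 12-month risk and leaving is unrelated to events. Protocol 8.3 lists serious adverse events and biopsy findings among the reasons for leaving, and events that come early or cause the exit shrink the gap.

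A third tempting inference is that non-hysterectomized women will appear safer by some fixed ratio. That would borrow 12-week dropout from another study part, which includes 15 mg and placebo arms, and would overlook the longer TEAE window. For AESIs an equal-risk comparison has little meaning, because the bleeding diary and the biopsies apply only to non-hysterectomized women.

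Finally, exposure (SAP 7.5) and disposition (SAP 7.2) are tabulated by status, so an imbalance would be visible. That is true, but neither first-event rates nor cumulative incidence can be derived from those tables.

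**Conclusion.** The point holds as a cheap improvement. Outside VTE and cardiovascular events, TEAEs, serious TEAEs and AESIs get no exposure-adjusted summary in a part where half the women are expected to leave. With constant, non-informative dropout the percentages are about 72% to 75% of the 12-month risk for risks of 2% to 50%. For a 10% risk the timing of dropout alone moves the displayed figure between 6.2% and 8.9%. These sizes rest on assumed event rates and dropout timing; the only planned input is the 50%.

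For the columns by hysterectomy status, the documents establish different observation windows and leave open different dropout. The size and direction of any net distortion are unknown, so no ratio should be claimed.

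**What to change.** In SAP 7.7.1.1 keep all counts and percentages, and add:

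- **Overview rows (overall and by hysterectomy status) and SOC rows of the overall TEAE table:** women with a first event per 100 patient-years, with an exact Poisson 95% CI. Person-time runs from Treatment Start Date to the first event or the end of the TEAE window, whichever is earlier. Label this as different from the VTE/cardiovascular person-time, which runs to end of treatment.
- **TEAE and serious-TEAE overview rows:** Kaplan-Meier cumulative incidence at Week 52, with the assumption of non-informative dropout stated.
- **AESIs:** give the rate in non-hysterectomized women only. Start person-time at the later of Treatment Start Date and the site's approval date for Protocol Version 6.0, because earlier AESIs were not collected retrospectively. Use no Week 52 cut-off: the scheduled end-of-treatment biopsy falls at Day 365 to 371 and would be missed. State the end date explicitly, since Protocol 10.6 ends AESI collection at the EoT visit and SAP 7.7.1.1 at the follow-up visit.

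The cost is a few extra columns and one short table. TEAE dates and the window are already derived; the AESI rows also need site approval dates. Rates for every preferred term by status are not needed and would go beyond the planned tables. The drawback is that a rate assumes a roughly constant hazard. The Kaplan-Meier figure covers this for the main rows, but AESI rates remain approximate because biopsy findings cluster at visits.
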